6 STUDY INTERVENTION

6.1 STUDY INTERVENTION(S) ADMINISTRATION

6.1.1 STUDY INTERVENTION DESCRIPTION

For the treatment of the auditory verbal hallucinations (AVH), we will use transcranial magnetic stimulation (TMS). Magnetic stimulation is a non-invasive technique used to excite and depolarize neurons in the brain and peripheral nervous system using induced currents. The excitation is caused by weak electric currents induced in the tissue by rapidly changing magnetic fields. The discovery is based on the principle of electromagnetic induction – discovered in 1831 by British scientist Michael Faraday.

When used to stimulate the brain it is normally referred to as TMS. TMS can be either single or paired pulse TMS or repetitive TMS (rTMS). Single/paired pulse TMS is mainly used for physiological research and diagnostic purposes. When the magnetic stimulation is delivered at regular intervals, it is termed rTMS. When stimulating the brain rTMS can produce lasting effects on cerebral functions, such as improvement of mood in depression (George and Belmaker, 2007).

Our TMS stimulator was manufactured by Magventure and fulfills the following quality assurances that can be found on their website (<https://www.magventure.com/en-gb/About/Quality-Assurance>):

"All products are developed and manufactured in accordance with the standard ISO 13485:2003, the current EU Medical Device Directive, the Canadian Medical Devices Regulation (CMDR), US 21 CFR 820 for the USA, and in accordance with a number of additional country-specific regulations. MagPro stimulators and magnetic coils are approved as medical devices in Europe, the USA, Canada, China, Japan, South Korea, Australia, Russia, and other markets worldwide."

That model that is used in our institute is the MagPro X30. This model is described to be "an advanced, high performance magnetic stimulator designed primarily for research purposes" with "a high quality tool for researchers with a large choice of stimulating parameters" and that has "stimulation rates up to 100 pps at high intensities and the possibility to combine waveforms and pulse modes" (<https://www.magventure.com>).

Auditory hallucination is the false perception of sounds. A common form involves hearing one or more voices, which is often associated with psychotic disorders such as schizophrenia. Despite intensive treatment with antipsychotic medication, the auditory hallucinations often persist.

It is anticipated that approximately 75 % of people diagnosed with schizophrenia experience AVH. Though, not all auditory hallucinations are associated with mental illness.

According to research, the AVH might occur as a result of over-activation of the left temporo-parietal cortex, which is the part of the brain responsible for speech perception (Rosenberg, Roth, Kotler, Zangen, & Dannon, 2011). Research indicates that rTMS is able to alter neural activity over the temporo-parietal cortex. Studies have shown that when rTMS is used as an adjunct to antipsychotic medication in treatment-resistant cases, the frequency and severity of auditory hallucinations can be reduced (Waters, Woodward, Allen, Aleman, & Sommer, 2010).

On clinicaltrials.gov it is possible to follow the development of ongoing clinical trials for treating auditory hallucinations disorder with rTMS. Treatment of auditory hallucinations with rTMS has not yet been approved by a regulatory body, and the treatment is considered investigational. Thus, we aim to test the efficacy of rTMS as a treatment for AVH in schizophrenia.

6.1.2 DOSING AND ADMINISTRATION

All patients receive 1Hz of rTMS over the area Spt four times on 1 day (1 pulse/second and a total of 1'000 pulses: 16 minutes' protocol at 100 % of motor threshold modified based on Hoffman et al.(Hoffman et al., 2003)). Area Spt will be localized via baseline structural imaging and our Localite TMS navigation system. Subjects will be withdrawn from the study if side effects become limiting, or if either the patient or principal investigator determine that rTMS should be discontinued.

6.2 PREPARATION/HANDLING/STORAGE/ACCOUNTABILITY

6.2.1 ACQUISITION AND ACCOUNTABILITY

TMS

The study's treatment will be performed with the TMS device of our institute at the Zucker Hillside Hospital. The procedure will be monitored by an MD and performed by trained staff.

Blood samples

The sample will be processed to extract the serum, which does not contain DNA, and plasma and residual samples will be immediately destroyed. The serum sample identified by the investigator generated unique identification number – hence not containing any PHI – will be sent to The Tom Cooper laboratory, Nathan Kline Institute, Orangeburg, New York.

6.2.2 FORMULATION, APPEARANCE, PACKAGING, AND LABELING

Blood samples

Each subject will be assigned a unique identification number generated by the research staff, and data will be coded using this number. The coded link to subjects' identities will be kept separate from the database in a locked file accessible only to the principal investigators. Hard copies of data will be stored in locked files in secure offices.

6.2.3 PRODUCT STORAGE AND STABILITY

TMS

The TMS device is stored in a lockable room and only used by trained staff.

Blood samples

The specimens of individuals for whom an extra vial of blood was extracted for potential serum antipsychotic concentration analysis that later do not consent to participate in the study will be destroyed immediately without being processed.

6.2.4 PREPARATION

Blood samples

The Tom Cooper laboratory, Nathan Kline Institute, which has extensive reputation in the field, will analyze the serum samples to obtain serum levels of Risperidone, Paliperidone, Olanzapine, Aripiprazole, Quetiapine, Ziprasidone, Lurasidone, Haloperidol, Fluphenazine, or Perphenazine (depending on relevance) using a validated liquid chromatographic method developed by the Cooper laboratory.

6.3 MEASURES TO MINIMIZE BIAS: RANDOMIZATION AND BLINDING

Patients who are willing to take part in the study and declining treatment by antipsychotic medication to sufficiently treat psychotic symptoms will be randomly assigned by the (trained) research coordinator to either sham or real rTMS following a permutation block randomization plan. The research coordinator

responsible for the randomization of patients, [name], will be unaware of what the next treatment assignment will be. Using this method of “concealed allocation of treatment assignment” ensures an unbiased randomization process. Double-blinding is ensured by the fact that the trained research assistant who is performing the rTMS treatments is not the same person (rater) who will conduct the psychopathology assessments. This way double-blinding is ensured in the sense that the rating is not influenced by the knowledge about the intervention arm (real or sham rTMS arm). This allows the unbiased assessment of changes in AVH severity due to rTMS without the prior knowledge of the rater whether the patient received real or sham rTMS. Patients declining medication will be randomly assigned to either the sham or the real rTMS group. For more detailed information on randomization see section 4.2.

For sham rTMS, the coil will be tilted by a 45-degrees angle. This procedure does not induce neuronal changes in the brain but still gives makes the characteristic noise produced during real rTMS stimulation.

Unblinding will only occur in the case of a serious adverse event or if patients wished to know after study completion in which study arm they have been. Unblinding will have to be approved by the PI first and can be done by the PI or the study coordinator.

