2.2 RISK/BENEFIT ASSESSMENT

2.2.1 KNOWN POTENTIAL RISKS

AVH symptomatology

Immediate risk

- Auditory verbal hallucinations can have different qualities such as being commenting, commanding, and/or threatening (e.g. harming oneself and others). These qualities can change over time and are thought to be related to factors such as stress (Upthegrove et al., 2016). AVHs during a phase of florid psychosis can have a more threatening character which in turn can lead to more stress and more psychotic symptoms. Therefore, a close monitoring of the patients' hallucinations, well-being, and the content of the AVH is important. All study personnel are trained to detect signs of stress in patients and worsening of psychotic symptoms. Additionally, the Believes About Voices Questionnaire (BAVQ-R) will be given to patients at every visit to assess the content, severity, and distress associated with AVH. Patients will be asked to report about their AVH's content and will be encouraged by the study coordinator to talk about changes in their mood and AVH content.
- In case a patient shows worsening of psychotic symptoms or, in the worst case, gets suicidal or homicidal within the three days of the study, participation is terminated and appropriate actions are initiated in accordance with the ward such as the application of antipsychotic medication given by the patient's treating clinician as per standard treatment guidelines and based on their best judgment. For this reason, the study staff will be in constant contact with the unit staff and the treating physician of the patient to work together with the best clinical interest for the patients' health.

Long-range risks

- There are no known long-range risks

Blood sample

Immediate risks

- We will obtain a blood sample to assess the serum concentration of the antipsychotic at the moment of hospitalization by adding an extra tube to the 2 that are routinely obtained via simple venipuncture as part of routine care in the emergency room. No phlebotomy will be performed at this point with a research indication if there is no clinical indication as per routine care. The additional blood sample will be collected in a third tube (approximately 2-3 mLs) from the same venipuncture for all patients that are hospitalized and potentially eligible to participate in the study. Therefore, the additional tube that is needed for the study does not constitute an additional risk.

Long-range risks

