3 OBJECTIVES AND ENDPOINTS

OBJECTIVES	ENDPOINTS	JUSTIFICATION FOR ENDPOINTS
Primary		
Examine the efficacy of low-frequency rTMS for the treatment of AVH in patients with a schizophrenia spectrum disorder.	Our primary outcome will be the score of the Hallucination Change Scale (HCS) (Hoffman et al., 2003). Response criteria: a) Clinically significant improvement in AVH is	The HCS is used as our primary outcome measure. The scale will be anchored at baseline using the narrative description of AVHs provided by the patient for the prior 24 hours, which will be assigned a score of 10. For subsequent assessments, the HCS ranges from 0-20 (with a score of 20

OBJECTIVES	ENDPOINTS	JUSTIFICATION FOR ENDPOINTS
	defined as a score of <8 on the HCS (Hoffman et al., 2013) b) Drop-outs: defined as patients who discontinue treatment before completing the 4 rTMS sessions.	corresponding to hallucinations twice as severe as baseline) (Hoffman et al., 2003; Hoffman et al., 2013). The HCS is a frequently used assessment for AVH in schizophrenia (Hoffman et al., 2003; Hoffman et al., 2013; Philipp Homan et al., 2011; P Homan et al., 2012). It is a feasible and time-efficient measure to assess severity of AVH on a daily basis and to evaluate improvement of AVH severity.
Secondary		
Monitor qualitative changes in AVH during the course of the rTMS treatment.	a) the qualitative content of AVH are assessed using the BAVQ-R to monitor changes in the content of AVH.	The BAVQ-R (CHADWICK, LEES, & BIRCHWOOD, 2000) is a self-report measure of patient's beliefs, emotions and behavior about AVH. This allows to assess changes in the quality of AVH over time and monitor if severity increases to the point of being dangerous for the patient or others (suicidal or homicidal tendencies).
Assessment of AVH as part of positive symptoms.	b) positive symptoms BPRS-subscale including "Hallucinatory Behavior", "Conceptual Disorganization", "Suspiciousness", and "Unusual Thought Content".	The positive symptoms BPRS-subscale is a well validated, often in studies used measure to assess positive symptoms including AVH (Robinson et al., 2015; Shafer, 2005).

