4 STUDY DESIGN

4.1 OVERALL DESIGN

This is a randomized, placebo controlled, double-blind clinical trial. We aim to assess the efficacy of rTMS as a potentially beneficial treatment option in drug-naïve patients and patients refusing antipsychotic medication who suffer from AVH. We use a novel protocol with only one day of treatment including 4 sessions of low-frequency rTMS and compare the effects with the sham stimulation. Further, we aim to examine structural and functional neurophysiological characteristics as predictors for rTMS.

As primary outcome, we aim to examine the efficacy of low-frequency rTMS for AVH in patients with a schizophrenia spectrum disorder with regard to AVH based on the HCS. Further, Hallucination quality (BAVQ-R), hallucinations as a part of positive symptoms (BPRS-subscale), clinical global improvement (CGI), and general assessment of functioning (GAF) are secondary outcome measures. Structural and functional neurophysiological characteristics (rCBF, resting fMRI, T1, and DTI) are investigated as potential predictors for rTMS treatment response.

In order to achieve these aims, we will have two intervention arms: real and sham rTMS. Patients who are willing to take part in the study and declining treatment by antipsychotic medication to sufficiently treat psychotic symptoms will be randomly assigned by the (trained) research coordinator to either sham or real rTMS.

Subjects will be randomized using a permutation block design to real rTMS or sham rTMS treatment. Accordingly, a well-documented double-blind randomization plan will be developed by the study's biostatistician and implemented in collaboration with the investigator. Copies of the resulting permutation blocks and randomization codes will be kept by the unblinded research coordinator. Blinded study personnel will not have access to these codes. When a new subject is randomized to a particular group, the research coordinator will provide written notice of the randomization condition of the subject to the operator of the rTMS.

Double-blinding is ensured by the fact that the trained research assistant who is performing the rTMS treatments is not the same person (rater) who will conduct the psychopathology assessments. This allows the unbiased assessment of changes in AVH severity due to rTMS without the prior knowledge of the rater whether the patient received real or sham rTMS.

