5.2 EXCLUSION CRITERIA

An individual who meets any of the following criteria will be excluded from participation in this study:

1. Therapeutic level of antipsychotic medication
2. ECT or rTMS within three months (see the TMS screening questionnaire)
3. History of seizures
4. Presence of implanted electronic device or metal implant in the head and neck region (DBS, cochlear implant, etc.)
5. Pregnancy, as assessed with a pregnancy test prior to every MRI measurement, or lactation
6. Any active general medical condition or CNS disease which can affect cognition or response to treatment
7. Treatment with another investigational drug or other intervention within 2 weeks
8. Current diagnosis of delirium, dementia, or amnestic amnesiac disorder; Diagnosis of mental retardation; Current (within the past three months) diagnosis of active substance dependence, or active substance abuse within the past week as indicated by self-report.
9. Patients who are cognitively impaired and are thus not able to give informed consent

Note, that other medication such as antidepressant, pain killers, or sleep medication are no exclusion criteria per se. Yet, if these medications are needed for the treatment of other mental illnesses such as subsumed under point 5 or 7 of the exclusion criteria then patients cannot be included in the study.

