7.2 PARTICIPANT DISCONTINUATION/WITHDRAWAL FROM THE STUDY

Participants are free to withdraw from participation in the study at any time upon request. Nevertheless, subjects may be prematurely terminated from the study if the investigators assess that the subject's clinical condition requires treatment(s) not available within the study context.

An investigator may discontinue or withdraw a participant from the study for the following reasons:

- Pregnancy as assessed with a pregnancy test before the two MRI measurements
- Significant study intervention non-compliance
- If any clinical adverse event (AE), laboratory abnormality, or other medical condition or situation occurs such that continued participation in the study would not be in the best interest of the participant
- Disease progression which requires discontinuation of the study intervention
- If the participant meets an exclusion criterion (either newly developed or not previously recognized) that precludes further study participation
- Participant unable to receive rTMS 4 times for one day
- If patients experience side effects that they are not willing to endure (such as headaches for example)
- Any medical condition which requires treatment with a medication with psychotropic effects
- Significant risk of suicidal or homicidal behavior (including aggressive behavior towards staff, others or themselves)
- MR Imaging contraindications
- Moving of patient or end of status as an in-patient at the Zucker Hillside Hospital

Duration of non-compliance will be determined by the trained study coordinator. Patients will be monitored closely by the study coordinator and all trained staff of the study. Changes i.e. in medication will be assessed before every visit/intervention.

If the patient had to have antipsychotics given because of an emergency or worsening of psychotic symptoms, then they are terminated from the study. However, we will also communicate on the ward that the patient's well-being is of main concern. Thus, should a patients' condition worsen and antipsychotics are thought to be the best help than medication should always be given regardless of the patient being enrolled in the study.

The reason for participant discontinuation or withdrawal from the study will be recorded on the Case Report Form (CRF). Subjects who sign the informed consent form and are randomized but do not

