8.3.3.3 EXPECTEDNESS

The PI as well as the research coordinator assisting the PI will be responsible for determining whether an adverse event (AE) is expected or unexpected. An AE will be considered unexpected if the nature, severity, or frequency of the event is not consistent with the risk information previously described for the study intervention.

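### Double-blinding is justified only by separating operator from rater; patient masking rests on a sham described as matching noise and is never checked, and the unblinded research coordinator who keeps the codes also assigns patients and handles adverse events

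*Combined protocol and SAP*

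**What the plan says.** **Basis of the blind.** Section 6.3 states: "Double-blinding is ensured by the fact that the trained research assistant who is performing the rTMS treatments is not the same person (rater", meaning the person who does the psychopathology assessments. It then explains that blinding is meant in the sense of a rating made without knowledge of the arm. Section 4.1 gives the same reason. Section 4.1 also has the operator told each subject's arm in writing.

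**Sham.** Section 6.3 tilts the coil by 45 degrees and says: "This procedure does not induce neuronal changes in the brain but still gives makes the characteristic noise produced during real rTMS stimulation". Sections 2.2.1, 4.1 and 8.2 foresee that rTMS may cause local scalp or face-muscle pain. Unblinding is limited to serious adverse events and patient requests after completion. It needs the PI's approval and is carried out by the PI or the study coordinator (6.3).

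**Primary outcome.** Section 3: "The scale will be anchored at baseline using the narrative description of AVHs provided by the patient for the prior 24 hours". That anchor is scored 10, and later scores run from 0 to 20. Trained raters do all assessments (8.1). The HCS is taken at baseline, after the last rTMS session and after the post-treatment MRI (1.1, 6.4).

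**Staff roles.**
- Research coordinator: assigns patients (4.1, 6.3). "Copies of the resulting permutation blocks and randomization codes will be kept by the unblinded research coordinator" (4.1). Is said not to know the next assignment (6.3). On expectedness: "The PI as well as the research coordinator assisting the PI will be responsible for determining whether an adverse event (AE" is expected or not (8.3.3.3). Also records reportable events with the PI (8.3.4).
- Study coordinator: patients "will be encouraged by the study coordinator to talk about changes in their mood and AVH content" (2.2.1). "Duration of non-compliance will be determined by the trained study coordinator" (7.2). May unblind with PI approval (6.3).

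**The concern.** The HCS measures change against the patient's own narrative. An expectation formed by the patient therefore shapes the report before a blinded rater hears it, and separating operator from rater cannot remove it. Two features make expectation plausible. Recruiting staff are to present rTMS persuasively as a promising new treatment (5.5). The first post-treatment HCS follows the last session, when any cue from four sessions with an operator who knows the arm is fresh.

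Section 9.2 says that a detected effect may be the basis for a larger study. If real rTMS looks better on the HCS, the plan collects nothing that bears on whether patients had recognised their arm, and that cannot be reliably recovered later.

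The second strand is staff knowledge. If the person who assigns patients can read the blocks, allocation concealment is in doubt. If the same person helps classify and record events, knowledge of the arm can enter the safety data.

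**Working it through.** **1. Who is blind, as far as the text says.**

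| Person | Status in the plan | Section |
|---|---|---|
| Rater | blind | 4.1, 6.3 |
| Patient | not stated; sham described as keeping the noise | 6.3 |
| rTMS operator | told the arm in writing | 4.1 |
| Research coordinator | unblinded, keeps blocks and codes | 4.1 |
| Study coordinator | not stated; may unblind with PI approval | 6.3 |
| PI | not stated; approves and may carry out unblinding | 6.3 |
| Outcome analyst | not stated | – |

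The one argument offered for double-blinding reaches only the first row.

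**2. The sham.** The description covers sound. Whether the tilted coil gives the scalp or muscle sensation of the real position is not addressed, although pain at those sites is foreseen. Nothing governs what the operator may say to the patient.

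**3. Check of the blind.** The schedule of activities (1.3), the assessments (8.1) and the analyses (9.4) contain no guess of arm by patient or rater.

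**4. Section 4.1 against 6.3.** In 4.1 the research coordinator keeps copies of the permutation blocks and codes. In 6.3 the research coordinator who randomises does not know the next assignment. Someone who holds the blocks can look it up, unless the copies are sealed or two people are meant. Neither section says so.

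**5. The plan's own figure.** Section 9.2 gives 40 patients for d = 0.9, 80% power and alpha 5%.
- Normal approximation: n per arm = 2(1.960 + 0.842)² / 0.9² = 15.70 / 0.81 = 19.4, so 20.
- Noncentral t: 20.39, so 21 per arm; power at 20 per arm is 79.2%.
- A one-sided test would need only 16 per arm, so the plan's figure is two-sided and is reproduced.

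**6. Illustration of stake, on an assumed bias.** Let expectancy favour real rTMS by δ SD with no true effect. With 20 per arm, a two-sided 5% t test has 38 degrees of freedom and noncentrality δ√(20/2) = 3.16δ.

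| δ (assumed) | Noncentrality | Rejects, either direction | Rejects in favour of real |
|---|---|---|---|
| 0 | 0 | 5.0% | 2.5% |
| 0.1 | 0.32 | 6.1% | 4.9% |
| 0.2 | 0.63 | 9.5% | 9.0% |
| 0.3 | 0.95 | 15.2% | 15.0% |
| 0.5 | 1.58 | 33.8% | 33.8% |

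The t test stands in for the repeated measures ANCOVA of 9.4.2, as it does in 9.2. No value of δ comes from the documents.

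**The case against.** The plan does protect the patient's blind to a degree. It has a sham that keeps the noise, limits unblinding, and keeps the codes from blinded staff (4.1). Raters are separate from the operator, and the trial is an exploratory pilot (5.5, 9.2). All of this stands, and it rules out several stronger readings that a reader might infer.

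- *That the patient is unprotected.* The sham and the limits on unblinding contradict this. The gap is that sensation is not addressed and the blind is not checked. Nor do the documents say that the tilted coil produces no sensation; they are silent.
- *That both coordinators have the codes.* This is documented only for the research coordinator. The study coordinator has a power to unblind that needs PI approval. Whether the two titles are one person cannot be told from the public text, where names in 5.5 and 6.3 have been removed. Section 10.1.7 also speaks of research coordinators in the plural.
- *That a coordinator decides who is withdrawn or whether an event was caused by treatment.* Section 7.2 gives the study coordinator the duration of non-compliance and leaves withdrawal to an investigator. Causality belongs to the examining clinician (8.3.3.2) or the PI (10.1.6). The research coordinator's documented part is expectedness and recording, and neither enters the HCS.
- *That everyone with earlier rTMS should be excluded.* The criterion is "ECT or rTMS within three months (see the TMS screening questionnaire", so patients with older exposure can enter and might recognise a difference. No exposure rate is given and recruitment is deliberately broad (5.5), so a wider bar would be a debatable trade-off.

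It is also fair that a guess made after the outcome partly reflects improvement and cannot by itself separate expectancy from effect. A guess taken before the final HCS could prime the remaining primary rating.

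**Conclusion.** The point holds in this form. The stated justification covers the rating only. Patient masking is not stated, is described as matched for noise, and goes unchecked, while the primary outcome is anchored on the patient's account. Separately, the unblinded research coordinator who keeps the blocks and codes also assigns patients, assists with expectedness and records events. Sections 4.1 and 6.3 do not agree on what that coordinator knows.

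The size of any bias cannot be derived from the documents. A reader might want to express expectancy as a share of the planned 0.9 SD effect. That would need a rate of correct guessing, an effect of belief on the HCS and an HCS standard deviation, none of which the plan gives. The error rates in the table show only how sensitive a 20-per-arm comparison is over an assumed 0.1 to 0.5 SD. The staff-role part assumes that a shared title means the same person.

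The change is worth making before enrolment. It is cheap, and guesses of arm cannot be reliably collected afterwards.

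**What to change.** 1. **Section 6.3 (and the parallel text in 4.1).** Replace the sentence that derives double-blinding from the operator–rater split with a plain statement: patient, rater and outcome analyst are blind to arm; the rTMS operator and the code holder are not. Give the status of the PI and of each coordinator by role.
2. **Codes and roles.** Keep blocks and codes with an existing person who has no patient contact, no event or compliance judgement and no outcome analysis, and who releases each assignment to the operator only. The biostatistician who draws up the plan (4.1) qualifies only if someone else analyses outcomes. Have existing staff without code access do expectedness judgements, event recording, conversations about voices and non-compliance determinations. Reconcile 4.1 with 6.3 on what the assigning coordinator knows, and say whether research coordinator and study coordinator are one role.
3. **Check of the blind.** After the last HCS only, record the patient's and the rater's guess of arm, with confidence and reason. Report by arm, descriptively, and note that guesses made after the outcome are partly driven by improvement.

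Cost: a small reallocation of tasks among existing staff, one case report form item at an existing visit, and guess data that may prove less favourable than the present claim.
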